Women of childbearing age will be asked to undergo a pregnancy test on the day of surgery and provide a negative result. The determination of whether the patient takes their anti-hypertensive on the day of surgery will be determined by the PAC's normal practice and will be unaltered by this study. Our goal would be to enroll and obtain data on 15 patients for each group: (Arm 1) ACE group, (Arm 2) ARB group, and (Arm 3) patients on any other class of antihypertensive agent for greater than two months. There will also be a fourth comparison group (Arm 4) consisting of up to the first 15 enrolled patients whose SBP does not drop below the 80% baseline threshold after intubation. It would be our intent to continue enrolling patients until a sample size of 15 patients for each of the 3 groups (Arms 1,2,3) have completed the protocol and received the trial medication. Once each of the three experimental arms of the study (Arms 1,2,3) have 15 patients, enrollment in the fourth comparison group (Arm 4) will cease regardless of whether or not it has met the 15 patient goal. Based on an estimated incidence of hypotension of 40-60% following induction of anesthesia, we expect to have to consent approximately 90 patients. This is to account for patients who do not meet study criteria, thereby reaching our goal of 45 experimental patients and the tentative 15 patient comparison group.¹

There will be a total of 5 blood samples taken at three time points throughout the duration of the study. Patients will have an IV line placed in the holding area prior to surgery. At this time, we will draw the first two 10cc blood samples (one for LC/MS analysis, one for RIA analysis) for study purposes while the patient is in the preoperative holding room. The RIA labs will be processed at Wake Forest Baptist Medical Center and is sponsored by a grant from the NHLBI of the NIH. , and the LC/MS labs will be analyzed through an external contracted laboratory to gain information for RAAS component testing. An initial set of vital signs including heart rate (HR),

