Following intubation and before initial surgical incision, the BP will be checked using a non-invasive BP cuff every minute for 10 minutes. If a SBP that is less than 80% of the baseline reading is detected, the clinical team will immediately cycle the BP cuff in order to confirm the presence of hypotension. At this point an infusion of Ang II will be initiated at 2 ng/kg/min through a peripheral IV (although the recommended starting dose of Ang II is listed as 20ng/kg/min, this dosing regimen is based on patients in shock. The package insert also states that doses as low as 1.25ng/kg/min may be effective). Starting at a low dose will be important since patients taking ACE inhibitors may be more sensitive to Ang II. The BP will be checked every minute. The half-life of angiotensin 2 is < 1 minute and time to peak pharmacologic affect is less than 30-35 seconds so it will be necessary to monitor the blood pressure once per minute. The infusion will be increased at the discretion of the clinical team based on the response of the patient until a SBP within 5% of the baseline SBP has been achieved (although the rate will not be increased by more than 15ng/kg/min at a time and the rate will not exceed 80ng/kg/min based on the package insert dosing instructions). If the patient remains hypotensive despite use of the maximum dose of angiotensin II, then angiotensin II will be discontinued, the patient will be excluded from the study, and the blood pressure will be treated using conventional vasopressors. If a patient experiences SBP < 80% baseline for greater than four consecutive minutes after initiating Ang II, then a rescue vasopressor such as phenylephrine will be administered. This will be important for patients taking ARBs as they may be less sensitive to Ang II.

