We will record the infusion rate of Ang II, anesthetic level (i.e. end tidal agent concentration), HR, SBP, diastolic blood pressure, mean arterial pressure, and SpO₂ every minute for the duration of the study period if an infusion was initiated. Once the SBP is within 5% of baseline or greater, the infusion will be continued at that rate for 5 minutes. If the measured SBP significantly exceeds the baseline SBP by $\geq 15\%$, the infusion will be reduced or halted at the discretion of the team taking care of the patient. After 5 minutes of reaching the target pressure of within 5% of baseline or greater the final infusion rate will be recorded. At this time the third and fourth blood samples (10cc LC/MS blood sample, along with a 10 cc RIA blood sample) will be taken to measure the serum levels of different RAAS components associated with normalization of the SBP under general anesthesia. The infusion of Ang II will be discontinued. This will mark the end of the dose finding trial for the patient. Further vasopressor administration will be at the discretion of the team taking care of the patient but will not include Ang II. A fifth and final 10cc blood sample for LC/MS RAAS testing will be drawn 30 minutes after incision.

If the SBP for any enrolled patient does not drop below 80% of baseline in the first 10 minutes after intubation, Ang II will not be administered. However, we will still perform LC/MS RAAS 10 minutes after intubation, and LC/MS RAAS sampling 30 minutes after surgical incision for up to 15 previously enrolled patients as a comparison group (Arm 4). Once Arm 4 reaches 15 patients, any subsequent patients that do not experience a drop in SBP < 80% baseline will be excluded from the study and their LC/MS blood samples that were previously drawn will be discarded. However, we intend to analyze the RIA blood samples for up to 90 patients and these samples will not be discarded.

Subjects selection criteria

The study will recruit adult general surgery patients with underlying essential hypertension undergoing general anesthesia for elective general surgery. Patients will be recruited dependent upon their antihypertensive medication into the following arms.

Arm 1: Patients must be on ACE inhibitors, in addition they can also be on other classes of antihypertensive medication except for ARB.

Arm 2: Patients must be on ARBs, in addition they can also be on other classes of antihypertensive medication except for ACEi.

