The largest overall commitment of time from the patient will be in the PAC at the time of recruitment. One of the PAC attendings, or investigators, or study personnel will interview the patient explain the study and attempt to recruit the patient if they are eligible. The study participant will have their questions answered. If patient agrees to participate a consent form will be electronically mailed or physically mailed, to patient. Patient will be asked to sign consent and return electronically or by physical mail. Once initial consent is received, (Giapreza) will be prepared and ready for use during surgery

On the day of surgery, the study participant will be identified in the holding area and a study representative will make sure that he or she has not changed their mind about participation and will answer any questions the study subject may have thought of since the interview in the PAC. Patient will be asked to physically sign consent in person on day of, prior to surgery. Labs will be drawn as described in the methods section.

The participant will then be taken to the OR. After appropriate monitors are placed, induction of general anesthesia will be accomplished with propofol, rocuronium, and/or succinylcholine. If there is a decrease in SBP greater or equal to 20% (as described in the methods section), Ang II will be administered starting at 2ng/kg/min. Ang II will be titrated until the SPB is within 5% of the baseline SBP (see methods section for exact details). The duration of Ang II administration will not exceed 20 minutes.

After the surgery, a study representative will see the patient in the post anesthetic recovery room (PACU) prior to discharge to evaluate for any adverse events. A follow-up phone call will also be made 7 days after the administration of angiotensin II to evaluate for any adverse events.

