The primary outcome will be the mean dose required to increase the SBP in these 3 cohorts with essential hypertension (ACE inhibitor, ARB, or those on another class of hypertensive agents) to within 5% of baseline or higher. 15 patients will be selected to follow suit with other similar dose finding trials with vasopressors.¹⁰ The mean dose required to elevate SBP from the nadir to within 5% of baseline for each group will be compared for significance using a student's t-test and Bonferoni correction for multiple comparisons to determine if different doses of angiotensin 2 are required in patients chronically on ACE or ARB inhibitors. The dose-response data will be analyzed with linear regression to construct a dose response curve relating dose and percent increase in SBP from the nadir in the setting of general anesthesia. We will perform descriptive statistics on the patient population. Secondary outcomes will be the mean value for different components of the RAAS system in all 4 populations at different times prior to and during the surgical epoch;

Human Subjects Protection

Subject Recruitment Methods

Patients will be identified for participation in the Preoperative Assessment Clinic (PAC) prior to the day of surgery. Patients will be recruited by investigators and/or the study coordinator with the participation and collaboration of PAC attending and other staff present in the clinic involved in this study. We will attempt to recruit qualified subjects in a non-biased manner. Privacy will be protected because subjects will be recruited in the process of a confidential preoperative evaluation in the PAC. If they choose not participate no research record will be created other than to indicate that they declined to participate and as such there will be no contact information to destroy.

Informed Consent

Signed informed consent will be obtained from each subject. Research study members involved in the study will obtain informed consent. A copy of the signed consent will be given to the subject.

Confidentiality and Privacy

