Appendix 1: Data Collection Form

Study ID: _____

**A dose finding trial for angiotensin II (Giapreza) in hypertensive adults on
angiotensin converting enzyme inhibitors and angiotensin receptor blockers
with anesthesia-mediated hypotension**

DATA COLLECTION SHEET

A dose finding trial for angiotensin II (Giapreza) in hypertensive adults on angiotensin converting enzyme inhibitors and angiotensin receptor blockers with anesthesia-mediated hypotension

Study ID: _____ Age: _____ ASA PS: _____

Gender: M / F UPT: + / - / NA

Surgery date: _____ Surgical procedure: _____

Attending Anesthesiologist: _____

Antihypertensive group: ACE / ARB / other

Antihypertensive medication: _____ Duration of therapy: _____

Preoperative creatinine: _____ Diabetes: No / NIDDM / IDDM

Peripheral vascular disease: Y / N

DVT prophylaxis: SCD / SQ heparin / SQ enoxaparin / other _____

STUDY ID: _____

A dose finding trial for angiotensin II (Glipreza) in hypertensive adults on angiotensin converting enzyme inhibitors and angiotensin receptor blockers with anesthesia-mediated hypotension

1) Holding room data (Time: _____)

Vital signs	HR	
	NIBP/MAP	
	SpO ₂	

Medications taken DOS

LC/MS RAAS sample in holding
 WFBH labs—blood AND urine
 Urine NOT collected (reason): _____

2) OR pre-induction/Baseline (Time: _____)

NIBP/MAP	
----------	--

Induction

Time: _____

(1.5 mg/kg propofol, 0.8 mg/kg rocuronium; avoid pressors)

3) OR post-intubation

Time post-intubation	NIBP/MAP	Confirmatory BP (If <80% baseline)
1 min		
2 min		
3 min		
4 min		
5 min		
6 min		
7 min		
8 min		
9 min		
10 min		

IF ATII infusion started, see next page

IV fluid total PRIOR to ATII administration: _____

Time angiotensin II infusion started: _____

Goal BP +/- 5% of baseline, time reached: _____

ATII infusion at goal BP for 5 minutes, then:

VS/data	HR	
	NIBP/MAP	
	SpO ₂	
	ET Isoflurane (%)	
	Final angiotensin II rate (ng/kg/min)	

LC/MS RAAS sample

LC/MS RAAS sample 30 minutes post-incision

Time infusion stopped: _____

IVF total AFTER ATII administration complete: _____

If no hypotension (< 80% baseline) encountered:

Move to group IV (first 15 patients only)
 LC/MS RAAS draw 10 minutes post-intubation
 LC/MS RAAS sample 30 minutes post-incision
 >>OR<<
 Exclude patient from LC/MS analysis
 Discard first LC/MS sample from holding area

STUDY ID: _____

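### The primary mean dose covers only patients who reach target, with no analysis rule for those who are rescued, stall at the cap or run out of time

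*Combined protocol and SAP*

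**What the plan says.** The Analytical Plan states: "The primary outcome will be the mean dose required to increase the SBP in these 3 cohorts with essential hypertension", the target being within 5% of baseline or higher. Arms are compared by t-test with a Bonferroni correction. No analysis population is named, and nothing is said about rescue, non-response or a missing dose.

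The rules that decide who has a dose are elsewhere:

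- **Maximum rate** (Methods and Measures, Design). Titration starts at 2 ng/kg/min, rises by at most 15 at a time and stops at 80. If the patient remains hypotensive there, "then angiotensin II will be discontinued, the patient will be excluded from the study".
- **Rescue** (Design). The rule begins "If a patient experiences SBP < 80% baseline for greater than four consecutive minutes after initiating Ang II, then a rescue vasopressor" and names phenylephrine as an example. It neither stops Ang II nor removes the patient.
- **Hold** (Design). "Once the SBP is within 5% of baseline or greater, the infusion will be continued at that rate for 5 minutes". The final rate is recorded after that hold.
- **Time limit** (Interventions and Interactions). "The duration of Ang II administration will not exceed 20 minutes".
- **Enrolment** (Design). Recruitment runs until "15 patients for each of the 3 groups (Arms 1,2,3) have completed the protocol and received the trial medication".
- **Data form** (Appendix 1). The final-rate box follows "ATII infusion at goal BP for 5 minutes, then". One branch begins "If no hypotension (< 80% baseline) encountered". The readable pages have no branch for goal not reached.

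**The concern.** A dose required to reach target exists only for a patient who reaches it. The plan removes one group of non-reachers, replaces non-completers by further enrolment, and is silent on the rest. Whether a patient contributes to the primary mean thus depends on how well the drug worked.

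This bears on the comparison as well as the label. Design itself expects ACE-inhibitor patients to be possibly more sensitive to Ang II and ARB patients less so. If that is right, the ARB arm loses more of its high requirements, and the t-test sees a smaller difference than exists. Where a rescued patient later reaches target, the recorded rate is what was needed on top of phenylephrine, not an Ang II requirement.

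**Working it through.** **1. The plan's own figure.** The consent target is 45 treated patients divided by the incidence of hypotension: 45/0.50 = 90, which reproduces (the stated 40-60% gives 113 to 75). It has no allowance for treated patients who must be replaced. If 10% or 20% were, it becomes 45/(0.9 x 0.5) = 100 or 45/(0.8 x 0.5) = 113.

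**2. What the text does with each patient who starts Ang II.**

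| Patient | Care rule | Analysis rule |
|---|---|---|
| Reaches target, holds 5 minutes | Final rate recorded | In the mean |
| Still hypotensive at 80 ng/kg/min | Ang II stopped | Excluded |
| At 80 ng/kg/min, SBP 80-95% of baseline | None, if hypotensive means <80% | None |
| Below 80% for more than 4 minutes | Rescue vasopressor; Ang II may continue | None |
| Not at target in time | 20-minute limit | None |

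**3. Timing.** At one maximum step per minute (assumed pace) the rate runs 2, 17, 32, 47, 62, 77, 80, so the cap is reached at minute 6. Rescue falls due after more than 4 minutes below 80%. At that pace a continuously hypotensive patient meets the rescue rule before the exclusion can apply. The hold leaves 20 - 5 = 15 minutes to reach target.

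**4. Cap alone, closed form.** The documents give no dose distribution. Assume the requirement is log-normal with median m and log SD 0.8, and let a = ln(80/m)/0.8.

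- Share above the cap = 1 - Φ(a): 0.5%, 4.2% and 19.3% at m = 10, 20 and 40.
- Mean among the rest = m·exp(0.32)·Φ(a - 0.8)/Φ(a). At m = 40: 55.1 x 0.526/0.807 = 35.9. At m = 20: 23.7.
- Difference between arms, 40 vs 20: 35.9 - 23.7 = 12.2. With everyone kept and values capped at 80: 44.5 - 26.0 = 18.5.

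**5. Adding rescue and the time limit, by simulation.** Further assumptions: linear response from a nadir uniform on 60-79% of baseline; fixed steps of 5, 10 or 15 once a minute; rescue if SBP is <80% at minute 5 or later; target by minute 15; 400,000 patients per cell. Ranges are over step size.

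| Median requirement | Not at target on Ang II alone | At least one in 15, 1 - (1 - f)^15 | Mean recorded rate, at-target patients | Mean requirement, all, capped at 80 |
|---|---|---|---|---|
| 10 | 0.5-2.1% | 7-27% | 15-22 | 13.7 |
| 20 | 4-11% | 47-84% | 23-31 | 26 |
| 40 | 19-36% | 96-100% | 32-43 | 44.5 |

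At median 5 the loss is at most 0.2%. The recorded mean is too high at 10, either way at 20 and too low at 40, because titration overshoot raises it while selection lowers it.

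Causes at median 40, for steps of 5/10/15: rescue 32/11/5%; cap with SBP 80-95% 0/8/14%; time limit 4/0/0%. No patient is below 80% at the cap without having met the rescue rule first.

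**6. Selection alone.** Against the same dose steps with no losses, the difference in arm means is about 9-12 instead of 17-18 (medians 20 vs 40), 8-10 instead of 11-12 (10 vs 20), and about 6 instead of 6-7 (5 vs 10).

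**7. Effect of the missing rule.** At median 40 with 5-unit steps, the arm mean is 32 if failures are dropped and 30 if they are entered at their last rate. It is 35-37 if rescued patients go on to target with phenylephrine worth 10-15% of baseline.

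**The case against.** Four points on the other side have force.

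- **Rescue is not exclusion.** A reader might infer that every rescued patient drops out of the mean. The text does not say so: such a patient can continue Ang II, reach target and be counted. For this group the defect is an undefined value, not established selection, so the loss percentages above apply only if rescued patients are left out.
- **The exclusion clause is narrow.** A reader might also infer that this sentence itself removes many patients. In the model it removes none before rescue. If hypotensive there means not at target, which is possible because the sentence follows the titration instruction, the 80-95% group does have a rule. The mean then still covers only patients who reach target.
- **High doses are not suggested.** Design starts at 2 ng/kg/min, notes that 1.25 may work, and treats 20 as a starting dose for shock. Nothing supports a median of 40. These are starting doses, though, and the Background calls the effective rate unknown, so a low requirement cannot be assumed either.
- **The upper ends come from fixed 5-unit steps.** Design lets the team titrate to response. With steps of 15, 10 or 5 according to SBP, failures fall to about 0.5%, 4% and 19% at medians 10, 20 and 40. Slower titration (5 units every two minutes) gives 10%, 32% and 65%. The pace is not specified.

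The infusion page of the data form is not readable here and may already capture rescue. None of this supplies the missing rule.

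**Conclusion.** The concern stands as a gap in the text: the primary mean is conditional on reaching target, may include rates mixed with phenylephrine, and has no rule for three foreseeable kinds of patient. Confidence in that is high, and it should be fixed.

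The size cannot be derived from the documents. On the stated assumptions it is negligible at median requirements near 10 ng/kg/min or lower and material near 40. Selection alone shrinks the between-class contrast if one class needs more drug. It would be wrong to conclude that the reported mean is biased low by a known amount, because overshoot acts in the opposite direction. Nor do the documents show that the t-test must be replaced.

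**What to change.** **Design.** Replace exclusion at the cap with: *Ang II stopped; retained in the analysis*. Define failure as not reaching 95% of baseline on Ang II alone because of the cap, the 20-minute limit or rescue. Enrolment may still run to 15 at-target patients per arm, which preserves the RAAS samples.

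**Analytical Plan.** Report failures by type and arm among all patients who start Ang II. Keep the mean dose and t-test, labelled *among patients reaching target on Ang II alone*, so that mixed rates stay out of the mean. Add one prespecified supporting comparison of all treated patients: either a Bonferroni-corrected rank test with failures ranked highest, or a Gehan test with failures censored at their last rate.

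With 15 at-target patients per arm and alpha 0.05/3 = 0.0167 (three pairs, two-sided 0.05 assumed), simulated power was:

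| Medians | t-test, at-target only | Rank test, failures kept | Gehan |
|---|---|---|---|
| 20 vs 40 | 23-27% | 42-52% | 43-46% |
| 10 vs 20 | 26-31% | 31-42% | 32-42% |

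Null rejection under this enrolment rule was 1.0-1.7% (rank) and 1.2-1.8% (Gehan).

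**Cost.** Wording, plus fields for rescue (yes/no, time) and reason stopped if the infusion page lacks them. Rate and SBP are already recorded every minute, and care does not change. At median 40 about 19-23 patients per arm must start Ang II to give 15 at target (15/0.81 to 15/0.64); the present rule implies the same if rescued patients do not count as completers.

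**Downsides.** The rank composite treats rescue and cap failure alike, although with 5-unit steps 45-77% of failures truly need 80 or less. It also depends on titration speed: with equal medians but 5-unit steps in one arm and 15-unit steps in the other, it rejects 2-42% of the time, Gehan 10-44% and the present t-test 14-27%. Making it the primary test is therefore optional.

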non-invasive blood pressure (BP), and oxygen saturation (SpO₂) will be checked in the holding room. We will also record all medications taken on the day of surgery. Once in the operating room and following placement of vital sign monitors, another non-invasive BP will be checked prior to anesthetic induction. This reading will be used as the baseline systolic blood pressure (SBP). Sequential Compression Devices (SCD) will be used for venous thromboembolism (VTE) prophylaxis during surgery and these will be applied prior to induction of general anesthesia. General anesthesia will then be induced with 1.5 mg/kg of propofol followed by 0.8 mg/kg rocuronium and the patient will be intubated. If the dose of propofol is inadequate to achieve loss of consciousness, additional propofol may be given at the discretion of the attending anesthesiologist. In addition, a rapid sequence induction and intubation may also be allowed if clinically indicated for the safety of the patient as determined by the attending anesthesiologist. Anesthesia will be maintained with isoflurane in fresh gas such as oxygen and/or air. No vasopressors will be administered at induction or during intubation unless the SBP is less than 80% of baseline for greater than 4 consecutive minutes. In that case, a rescue vasopressor such as phenylephrine will be given.

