Arm 3: Patients on any other antihypertensive medication, and must not be on an ACEi or ARB.

Arm 4: Patients who qualify for arm 1, 2, or 3 but whose SBP does not drop below 80% of baseline in the first 10 minutes after intubation.

- **Inclusion Criteria**

- Diagnosis of hypertension and treatment for greater than 2 months and on the following medications
 - ACE inhibitors, in addition they can also be on other classes of antihypertensive medication except for ARB
 - ARBs, in addition they can also be on other classes of antihypertensive medication except for ACEi
 - Any other antihypertensive medication, and must not be on an ACEi or ARB
- Patients undergoing general anesthesia
- American Society of Anesthesiologists physical status 1-3
- Age ≥ 40 given that hypertension is not prevalent below this age

- **Exclusion Criteria**

- American Society of Anesthesiologists physical status 4-6
- BMI > 40
- History of deep venous thrombosis / thromboembolic disease
- History of stroke,
- Baseline SBP of ≥ 160 mmHg,
- History of myocardial infarction or cardiac stents
- Difficult airway
- Asthma
- Diagnosis of congestive heart failure of any stage, regardless of preserved or reduced ejection fraction; this includes both systolic heart failure and diastolic heart failure;
- Diagnosis of chronic obstructive pulmonary disease of any stage; this includes diagnoses of chronic bronchitis and emphysema
- Pregnant patients (safety of Ang II in pregnancy is unknown)

- Patients at increased risk for venous thromboembolic events such as current diagnosis of cancer and/or diagnosis of blood clotting disorders
- **Sample Size**
Our goal would be to enroll and obtain data on 15 patients for each group: ACE group, ARB group, and patients on any other class of antihypertensive agent for greater than 2 months. In addition, we would like to obtain data for up to 15 patients in the comparison group (Arm 4). The sample size was chosen due to its similarity to the ATHOS II dose-finding trial.⁹ It would be our intent to continue enrolling patients until a sample size of 15 patients for all 3 experimental groups has been reached. Based on an estimated incidence of hypotension of 40-60%, we expect to have to consent approximately 90 patients.¹ This is not a multisite study.

Interventions and Interactions

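### Arm 4 is assigned from post-intubation SBP alone, so a patient already rescued with a vasopressor at induction can enter the comparison group

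*Combined protocol and SAP*

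**What the plan says.** Arm 4 is defined in two places in the combined protocol and SAP. The Design section describes up to the first 15 enrolled "patients whose SBP does not drop below the 80% baseline threshold after intubation". Subjects selection criteria adds the time window: patients who qualify for Arms 1 to 3 but "whose SBP does not drop below 80% of baseline in the first 10 minutes after intubation". The Design section uses the same window for the decision not to give Ang II. None of these texts mentions the period before intubation or prior vasopressor use.

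The Design section does foresee hypotension in that earlier period: "No vasopressors will be administered at induction or during intubation unless the SBP is less than 80% of baseline for greater than 4 consecutive minutes". It continues: "In that case, a rescue vasopressor such as phenylephrine will be given". The readings that decide the arm start later: "Following intubation and before initial surgical incision, the BP will be checked using a non-invasive BP cuff every minute for 10 minutes".

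Appendix 1 (Data Collection Form) routes patients to group IV under the heading "If no hypotension (< 80% baseline) encountered", which carries no time window. As far as the form can be read, its induction block holds a time and a drug reminder. It has no field for SBP between induction and intubation, or for a rescue vasopressor.

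The Analytical Plan uses Arm 4 only for the secondary outcome, mean RAAS components in all four groups. The primary outcome is the mean Ang II dose in Arms 1 to 3.

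**The concern.** Arm 4 gives the RAAS profile of patients whose pressure held, for comparison with those whose pressure did not. A patient who spent more than 4 minutes below the threshold and was brought back by a vasopressor belongs on the other side of that contrast. In addition, this patient's 10-minute RAAS sample would be drawn after a vasopressor that the other Arm 4 patients did not receive.

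There is a related exposure in Arms 1 to 3. If the rescued patient drops again after intubation, Ang II is titrated with another vasopressor possibly still acting, and the final rate enters the primary mean as if Ang II alone had restored the pressure. The Design section also allows rescue after Ang II has started, with the same possible effect. It singles out ARB patients as those for whom that provision will matter. The Analytical Plan has no rule for either case.

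**Working it through.** **1. The plan's own figure.** Inputs: 3 arms × 15 = 45 treated patients, and a hypotension incidence of 40-60% (Design; Sample Size). Number to consent = 45 / incidence. At 50%, 45 / 0.50 = 90, which reproduces the stated figure of about 90. The ends of the range give 45 / 0.40 = 112.5, or 113, and 45 / 0.60 = 75. At 50%, 90 − 45 = 45 patients would not receive Ang II and are candidates for 15 Arm 4 places.

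**2. Following the rules for each possible course.**

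| Course | Arm by the definitions | Form heading, read without a window |
|---|---|---|
| Never below 80% | 4 | 4 |
| Below 80% for over 4 min before intubation, rescued, then at or above 80% for 10 min | 4 | Not 4 |
| Same, but falls again after intubation and is confirmed | 1, 2 or 3, another vasopressor possibly acting | Not 4 |
| Brief dip before intubation, no rescue, then at or above 80% | 4 | Not 4 |
| First falls after intubation, Ang II started, then over 4 min below 80% | 1, 2 or 3, rescued during titration | Not 4 |

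The second row is the problem. The only exclusion tied to failed pressure control concerns patients still hypotensive on maximum Ang II, so it does not reach this patient. Interventions and Interactions ties Ang II to a fall of 20% or more, but refers back to the methods and so does not settle the matter.

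**3. Weight of one patient.** 1 / 15 = 6.7% of an arm. If k patients in an arm of 15 have a recorded rate lowered by d, the arm mean falls by k × d / 15. As an illustration only, take k = 1 and d = 15 ng/kg/min, the largest single increase the protocol permits: 1 × 15 / 15 = 1 ng/kg/min.

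**4. How many, under assumption.** The documents give no rate. Let r be the share of consented patients who are rescued before intubation and then stay at or above 80%. The share of Arm 4 affected is q = r / (1 − incidence), the expected number is 15q, and the chance of at least one is 1 − (1 − q)^15. At 50% incidence:

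| r (assumed) | q | Expected of 15 | Chance of at least one |
|---|---|---|---|
| 2% | 4% | 0.6 | 46% |
| 5% | 10% | 1.5 | 79% |
| 10% | 20% | 3.0 | 96% |

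Across 40-60% incidence the expected number runs from 15 × 0.02 / 0.60 = 0.5 to 15 × 0.10 / 0.40 = 3.75. These values show sensitivity to r; they do not estimate it.

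**5. Room for the change.** Candidates left after removing such patients = N × (1 − incidence) − r × N. At 50% incidence and r = 10%: 45 − 9 = 36. In the tightest case tried, 60% incidence with N = 75 and r = 10%: 30 − 7.5 = 22.5. Both exceed 15.

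**The case against.** The strongest reply is that Arm 4 is an operational group, those who did not meet the Ang II trigger, and is defined consistently as such. On this view no text says that its members were never hypotensive, and the one text that comes close, the form heading, would keep a rescued patient out. That is fair as far as it goes. But the heading follows the table of post-intubation readings, and the formal definitions are explicit about their window. At best the texts conflict, and the heading does not cure the gap.

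The reply on frequency also stands. Once the post-intubation readings begin, a confirmed low reading starts Ang II. Rescue before Ang II therefore needs more than 4 consecutive minutes below 80% before those readings take over. To reach Arm 4 the patient must then hold for another 10 minutes. This may be uncommon, and nothing in the documents anchors the rates in the illustration.

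A reader might infer that the primary dose comparison is biased toward a false conclusion. The documents do not support that. Arm 4 is not in that comparison. In Arms 1 to 3, a spurious difference between arms would require rescue, or its effect, to differ by arm. The remark about ARB patients makes that conceivable for rescue during titration, but gives no figure. Nor do the documents say how long a rescue agent acts, and a patient rescued early must fall again, be titrated to target and be held there for 5 minutes before the rate is recorded.

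A reader might also infer that any reading below 80% should bar a patient from Arm 4. The Design section calls for a repeat reading to confirm hypotension, and a bar on single readings would leave patients with brief or unconfirmed dips in no group at all.

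**Conclusion.** The gap is real and modest. Followed literally, the Arm 4 definition admits patients who had sustained hypotension and received a vasopressor before the classifying window opened, while the form heading suggests otherwise. The established effect is on group composition in the secondary RAAS comparison, where each such patient is 6.7% of a full Arm 4. An effect on the primary outcome is possible but not shown: a vasopressor given before or during Ang II titration may lower the recorded rate. The number of patients is unknown and may be small. The conclusion rests on the wording of the definitions and the rescue provision, not on any assumed rate. It is worth correcting because the correction is cheap, and because the form, as it can be read, would not identify the patients rescued before intubation afterwards.

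**What to change.** 1. Add to the Arm 4 definition, in both places and on the form: *and who received no vasopressor from induction to 10 minutes after intubation*. Report patients whom this clause keeps out and who never receive Ang II (under the written rules, those rescued before intubation) as a separate category. Patients with only a brief or unconfirmed low reading stay in Arm 4 but are flagged. Reword the form heading to match.
2. Add two fields to the data form: lowest SBP between induction and intubation, and any vasopressor given, with time and dose.
3. Repeat the primary dose analysis without patients given any non-study vasopressor between induction and recording of the final Ang II rate, including during titration, and report the number excluded per arm. Keep this as a sensitivity analysis beside the main one, since patients rescued during titration may be those who respond least to Ang II.

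Rescue treatment is unchanged. The cost is one clause, two form fields and one sensitivity analysis. The downside is that an occasional patient no longer counts toward Arm 4. On the figures above, at least 22.5 candidates would remain for 15 places, so the number to consent should not rise.
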